8.1. Statistical analysis

Summary statistics will be generated to describe the study sample at baseline. Descriptive statistics, including measures of central tendency (e.g. means, medians) and estimates of spread (e.g., standard deviations, quartiles) will be used for continuous variables such as age and baseline HBV DNA and HBsAg levels. Frequency distributions will be used for categorical variables such as HBV genotype and HBeAg status. Ninety-five percent confidence intervals will be calculated for all point estimates of continuous data. Graphical displays (e.g. histograms, box plots) will also be used to describe the data. The baseline demographic information and viral characteristics will be compared between the two treatment arms using the chi-square test for association or exact tests for differences in proportions for categorical variables or using a test of trend

in ordinal data. Continuous variables may be transformed, where appropriate, to meet the assumptions of parametric tests. The Student's t-test or a non-parametric alternative, the Wilcoxon rank-sum test, will be used to determine differences in the distribution of continuous data between the two treatment arms.

Primary analyses will be performed using all enrolled participants (intention-to-treat analysis). Participants will be considered enrolled in the study upon being randomized to one of the two treatment arms.

For all analyses, a p-value of less than 0.05 will be used to indicate statistical significance.

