Time to such events may also be of interest (e.g. cumulative HBeAg loss, time to treatment failure). For time-to event analysis, Kaplan-Meier curves will be used to plot the cumulative proportion of events over time by treatment groups. The cumulative proportions will then be compared using two-sided stratified log-rank test. The treatment effect will be described using hazard rate of the event and corresponding 95% confidence interval. In order to take into account the stratification at randomization, we will use stratified Cox proportional hazard models. Comparison of hazard rates of an event across two treatment groups adjusting for other baseline demographic, virological and clinical characteristics such as age, race, genotype, HBeAg status, initial HBV DNA level, and baseline histology will be performed using Cox proportional hazard regression. The results will be presented using hazard rates and 95% confidence intervals.

The second group of endpoints is continuous variables such as changes in ALT, HBV DNA levels from baseline at designated treatment or follow-up time points. Descriptive statistics, including measures of central tendency (e.g. means, medians) and estimates of spread (e.g., standard deviations, quartiles) will be used to characterize such changes. Student's t-test or a non-parametric alternative, the Wilcoxon rank-sum test, will be used to determine differences in the distribution of these changes between the two treatment arms. Multiple regression analyses will be conducted to assess the association between baseline characteristics and these changes. Spearman or Pearson correlation coefficients will be used to measure the strength and direction of the association between such changes and other participant characteristics. Scatter plots will be used to display the association between continuous variables.

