The third group of variables consists of variables that are measured over time (longitudinal data) such as quantitative HBV DNA levels. For graphical representation over time, we will use spaghetti plots of original data (e.g. HBV DNA levels) and summarize the pattern of data across subgroups (e.g. genotype, treatment groups) over time by using means (for continuous outcome) or proportions (for binary outcomes). To determine the significance of change in continuous outcome over time across treatment group adjusting for other baseline and longitudinal participant characteristics, we will use mixed models if the data are normally distributed or generalized estimating equations (GEE) if deviation from normality is evidenced. These approaches simultaneously model the regression of the response variable on the independent variables and account for the correlated nature of the responses. Analyses using conventional regression methods could provide erroneous variance estimates and loss of statistical efficiency because of the conventional assumption that each response is statistically independent. As a result, invalid inferences could be made if the conventional approach were applied to these longitudinal data. A similar approach of analysis will be adopted (generalized linear mixed model or GEE) for longitudinal binary or count outcomes over time.

The results will be summarized using rate of change/odds ratio/relative risk over time and the corresponding confidence intervals. Interaction between treatment and participant characteristics will be investigated to assess the differential effect of treatments across subgroups of participants (e.g. genotypes).

Secondary endpoints that are defined within a specific subgroup will be analyzed only for participants in that subgroup. For example, sustained off treatment (36 and 48 weeks after end of treatment) responses will be assessed only among those whose treatment was discontinued at week 192.

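### Changes in ALT and HBV DNA at fixed time points are compared without the baseline value or the randomisation strata; adjusting for them is a free gain in precision

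*Combined protocol and SAP*

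**What the plan says.** Section 8.1.2.1 sorts the remaining secondary outcomes into groups. On the group at issue it states: "The second group of endpoints is continuous variables such as changes in ALT, HBV DNA levels from baseline at designated treatment or follow-up time points". For the comparison of arms it states that a t-test or a Wilcoxon rank-sum test "will be used to determine differences in the distribution of these changes between the two treatment arms". No covariate, no stratification factor and no rule for choosing between the two tests is given. The regression planned for the same quantities has another purpose: "Multiple regression analyses will be conducted to assess the association between baseline characteristics and these changes". Treatment arm is not named as a term in it.

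A third group follows, described as "variables that are measured over time (longitudinal data) such as quantitative HBV DNA levels". Its stated aim is "To determine the significance of change in continuous outcome over time across treatment group adjusting for other baseline and longitudinal participant characteristics", and for this "we will use mixed models if the data are normally distributed or generalized estimating equations (GEE) if deviation from normality is evidenced". HBV DNA is named there and ALT is not. The text does not say whether the outcome's own baseline value or the randomisation strata enter the model.

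Elsewhere the plan does use this information. Section 8.1.2 uses a stratified log-rank test and stratified Cox models for cumulative HBsAg loss. Section 8.1.2.1 uses a Mantel-Haenszel test for binary endpoints and stratified log-rank and Cox methods for event times. Each of these also has a covariate-adjusted treatment comparison that includes initial HBV DNA.

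**The concern.** The information needed for a better comparison is already collected. ALT (in the hepatic panel) and HBV DNA are measured at day 0 (section 6.3). HBeAg status, genotype A versus others, and cirrhosis are the randomisation strata (section 3). A change score subtracts the whole baseline value, whatever its actual relation to follow-up, and so carries baseline noise into the treatment contrast. ANCOVA estimates that relation and removes only what baseline predicts.

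The protocol's own content suggests that baseline variation is large compared with follow-up variation. Eligible ALT spans a tenfold range (above 45 and up to 450 U/L in males, above 30 and up to 300 U/L in females; sections 4.1 and 4.2). Eligible HBV DNA has a lower limit of 1000 IU/mL and no upper limit (section 4.1). Section 1 expects 80-90% of patients on long-term treatment to reach marked HBV DNA suppression and normal ALT. If follow-up values converge in this way, much of the variation in change is variation in baseline. At stake are wider confidence intervals than necessary and greater exposure to chance baseline imbalance, on supportive outcomes.

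**Working it through.** **1. The plan's own figure.** The only sample size (section 8.3, Sample size and power) concerns the primary binary endpoint: 5% versus 15%, two-sided 5% level, 80% power. With pooled variance under the null:

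n per arm = [1.96·√(2·0.10·0.90) + 0.8416·√(0.05·0.95 + 0.15·0.85)]² / 0.10² = 140.1, rounded up to 141.

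Then 2 × 141 = 282, and 282 / 0.75 = 376. The stated figures reproduce and do not depend on this point. The documents state no sample size, SD or correlation for change in ALT or HBV DNA, so everything below rests on assumed values.

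**2. Formula.** Scale the baseline SD to 1. Let k be the follow-up SD divided by the baseline SD, and ρ the baseline/follow-up correlation, both the same in each arm. Per participant:

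- change-score variance: 1 + k² − 2ρk
- ANCOVA residual variance: k²(1 − ρ²)
- difference: (1 − ρk)², which is never negative, so in large samples ANCOVA is never less precise

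The ratio of ANCOVA to change-score variance is k²(1 − ρ²) / (1 + k² − 2ρk). At k = 1 it reduces to (1 + ρ)/2.

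**3. Equal SDs (k = 1, assumed).** Take 141 evaluable per arm, with the effect set so that the unadjusted t-test on change has 80% power. Power after adjustment is Φ(2.8016/√ratio − 1.96).

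| ρ (assumed) | variance ratio | reduction | power with ANCOVA | n per arm for the same precision |
|---|---|---|---|---|
| 0.3 | 0.65 | 35% | 93.5% | 92 |
| 0.5 | 0.75 | 25% | 89.9% | 106 |
| 0.7 | 0.85 | 15% | 86.0% | 120 |
| 0.9 | 0.95 | 5% | 82.0% | 134 |

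Simulation (4000 runs each) agrees: 80.9% for the t-test against 93.7% for ANCOVA at ρ = 0.3, and 79.9% against 89.7% at ρ = 0.5.

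**4. Follow-up SD half the baseline SD (k = 0.5, assumed).**

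- ρ = 0.3: 0.25·0.91 / 0.95 = 0.239
- ρ = 0.5: 0.25·0.75 / 0.75 = 0.250
- ρ = 0.7: 0.25·0.51 / 0.55 = 0.232
- ρ = 0.9: 0.25·0.19 / 0.35 = 0.136

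The ratio is then about 0.14 to 0.25, a much larger gain than with equal SDs. Any further gain from the strata is not counted in steps 3 and 4.

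**5. What the longitudinal model could recover.** This depends on how it is specified. If baseline is a covariate, or a response with a mean common to both arms, the model captures essentially the ANCOVA gain. If baseline is one of the repeated responses with a separate mean in each arm, then with complete data and an unstructured covariance the contrast at a given visit is the difference in mean change again, and nothing is gained from the baseline value. The plan does not say which applies.

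**6. Open choice of test.** If an analyst always reported the smaller of the two p-values, simulated type I error would be about 6.3% with normal data and 7.7% with heavy-tailed changes, against 5%.

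**The case against.** The strongest reply is that the plan already contains an adjusted comparison of arms. A reader might infer from the t-test sentence that ALT and HBV DNA receive no adjusted continuous analysis at all. The documents do not support that: the longitudinal model compares treatment groups with covariates, and its mention of HBV DNA is only an example. ALT would qualify, since both are measured at every on-treatment visit (section 6.4). This stands, and it narrows the point to what that model leaves unsaid.

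A reader might also infer that stratified randomisation is ignored for ALT and HBV DNA in general. It is not. In sections 2.2.1 to 2.2.9 they enter as thresholds, and those binary endpoints get a Mantel-Haenszel test and adjusted regression.

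Nor is the comparison biased: the arms are randomised, so the unadjusted difference is valid and only precision is lost.

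It is tempting to quote a single gain of 25% to 35%. That needs equal SDs and a correlation of 0.3 to 0.5, and the documents support neither. The true gain could be much smaller or much larger.

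The open choice of test is minor. Nothing in the plan proposes reporting the smaller p-value. The implied criterion is distributional, as the general paragraph on baseline comparisons suggests: "Continuous variables may be transformed, where appropriate, to meet the assumptions of parametric tests". The figures in step 6 are a worst case and not an expected error rate.

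Finally, a rank test is a reasonable answer to HBV DNA values piled up below the limit of quantification. That also stands, and the fix allows for it.

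**Conclusion.** The point holds as a free improvement. The fixed-time comparison of change in ALT and HBV DNA uses neither baseline nor strata, unlike the plan's treatment of its binary and time-to-event endpoints, and the longitudinal model as worded may make up only part of the difference. With equal SDs the variance reduction runs from 35% at a correlation of 0.3 to 5% at 0.9. With the follow-up SD at half the baseline SD, the variance ratio is about 0.14 to 0.25. Both SD ratios and all correlations are assumptions, and the formulas also assume a common SD and correlation across arms. The consequence is confined to supportive continuous outcomes that are not itemised in sections 2.2.1 to 2.2.9. The primary analysis, the 376 participants and the validity of the comparison are untouched.

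**What to change.** Adopt one of two changes in section 8.1.2.1.

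- **Replace the t-test/Wilcoxon sentence.** At each designated time point, analyse log10 HBV DNA and log ALT by ANCOVA on arm, the baseline value on the same scale, and the three strata (HBeAg status, genotype A versus others, cirrhosis). State in advance how HBV DNA below 20 IU/mL is handled. Keep a stratified rank test as sensitivity analysis, and make it the main analysis for HBV DNA at time points where most values are below that limit.
- **Or declare the longitudinal model the main comparison of arms.** Name ALT as well as HBV DNA, state that the outcome's own baseline value and the three strata are included, and use baseline covariates only for the treatment contrast. The same rule for values below 20 IU/mL is needed.

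Either change also settles which analysis is the main one. The cost is SAP wording, ideally fixed before data by arm are examined. No extra visits, samples or participants are needed.

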Thus, the advantages of nucleos(t)ide analogue therapy are the ease of administration, the lack of significant side effects and the consistent suppression of HBV DNA that can be achieved, particularly with the newer agents such as tenofovir DF and entecavir. While emergence of drug resistance can limit the efficacy of oral agents, a low rate of antiviral resistance (1% or less even with prolonged therapy for 4 to 5 years), is seen with entecavir and tenofovir DF, reflective of their greater potency and higher genetic barrier to resistance. As a consequence 80-90% of patients treated long-term with these agents achieve rates of marked suppression of HBV DNA levels and normal ALT levels. The advantage of peginterferon therapy is that it is administered for a limited period (6 to 12 months) and results in loss of HBsAg in a significant proportion of patients. Previous studies have shown that a one-year course of combination therapy of peginterferon and nucleos(t)ide analogue does not yield a higher response rate than a one-year course of either agent alone (21). However, these studies have been limited by the use of a nucleos(t)ide analogue with high risk of resistance (e.g. lamivudine) and a relatively short course of treatment. Thus, an obvious question is whether the combination of a limited course of peginterferon (6 or 12 months) with long-term therapy with a potent nucleos(t)ide analogue (tenofovir DF or entecavir for at least 4 years) will provide a higher rate of loss of HBsAg and ability to stop therapy without relapse. This clinical trial compares the efficacy of peginterferon plus a potent nucleotide analogue, tenofovir DF, for 24 weeks followed by monotherapy with tenofovir DF for a further 3.5 years to the efficacy of that same potent nucleotide analogue, tenofovir DF, given for a full 4 years. The primary measure of outcome will be HBsAg loss in serum 240 weeks after starting antiviral therapy.

2. Study objectives

To define the role of limited duration peginterferon alfa-2a in the presence of tenofovir for treating people with chronic hepatitis B by:

- Evaluating “off treatment” sustained responses following combination therapy consisting of peginterferon alfa-2a plus tenofovir DF versus tenofovir DF monotherapy.
- Comparing the on-treatment efficacy of initial treatment with combination therapy consisting of peginterferon alfa-2a plus tenofovir DF versus tenofovir DF monotherapy.

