8.3. Sample size and power

The sample size for this study was determined based on the primary endpoint of HBsAg-loss at 48 weeks after treatment has been stopped. There are no data available on HBsAg loss for long-term treatment with tenofovir DF or tenofovir DF and peginterferon combination therapy. We anticipate that after 192 weeks of treatment and 48 weeks of follow-up post-treatment 5% of the participants in the tenofovir DF alone group will achieve HBsAg loss compared to 15% participants in the tenofovir DF and peginterferon combination therapy group. The clinical trial would require 141 participants per arm (282 participants in total) to detect this expected difference with 80% power at 5% level of significance using a two-sided test of equality between two proportions (chi-square test). However, for this long-term treatment trial, it is expected that approximately 25% of the participants will be lost to follow-up and hence the study will recruit a total of 376 participants (randomized 1:1 to two treatment arms, 188 per arm) to account for the missing participants.

9. Data and safety monitoring board

Data and safety will be monitored by the NIDDK in conjunction with an NIDDK-appointed Data and Safety Monitoring Board (DSMB). This board serves in a consultative capacity to inform the NIDDK decisions regarding conduct of the study. The description of DSMB activities is included in the DSMB Charter.

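### Change in HBV DNA and ALT is related to participant characteristics without requiring the starting value, so for HBV DNA a characteristic tied to the starting level can look predictive only because of that level

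*Combined protocol and SAP*

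**What the plan says.** Section 8.1.2.1 treats changes from baseline in ALT and HBV DNA, at designated on-treatment or follow-up weeks, as a second group of endpoints. After the between-arm t-test or Wilcoxon test it plans two analyses of who changes more:

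- A regression: "Multiple regression analyses will be conducted to assess the association between baseline characteristics and these changes". No covariates are listed for it.
- Correlations: "Spearman or Pearson correlation coefficients will be used to measure the strength and direction of the association between such changes and other participant characteristics". As written, these are bivariate.

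For the event models, Sections 8.1.2, 8.1.2.1 and 8.2 give example adjustment covariates: "age, race, genotype, HBeAg status, initial HBV DNA level, and baseline histology". Initial HBV DNA is among them. Baseline ALT is not, in any of these places.

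Section 8.1 sets the threshold: "For all analyses, a p-value of less than 0.05 will be used to indicate statistical significance". The change-score associations are therefore not marked as descriptive.

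Section 1 says of entecavir and tenofovir DF that "80-90% of patients treated long-term with these agents achieve rates of marked suppression of HBV DNA levels and normal ALT levels". It also describes HBV DNA as high or somewhat lower in the HBeAg-positive phases and moderate in HBeAg-negative disease.

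**The concern.** The clinical question is whether a characteristic goes with a better response. The quantity tested is its association with follow-up minus baseline. The baseline value is part of that difference, so anything correlated with baseline is correlated with change even if it says nothing about where the participant ends up. The effect is strongest when follow-up values are squeezed towards a floor, which is what the Background leads one to expect for HBV DNA on tenofovir: change is then close to a constant minus the baseline.

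At stake is how the predictor results are read. A group that starts higher could be described as responding better virologically when it reaches a low level no more often, or even less often, than the other group.

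**Working it through.** **The plan's own figure.** The documents give no figure for these analyses, so only the number of completers is taken from them. Section 8.3 states: "The clinical trial would require 141 participants per arm (282 participants in total) to detect this expected difference with 80% power at 5% level", "using a two-sided test of equality between two proportions (chi-square test", with "5% of the participants in the tenofovir DF alone group will achieve HBsAg loss compared to 15% participants". The pooled-variance formula gives [1.96√(2×0.10×0.90) + 0.842√(0.05×0.95 + 0.15×0.85)]² / 0.10² ≈ 140.1, so 141 per arm. That reproduces the plan, and 282/0.75 = 376 recruited. I use n = 282.

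**General formula.** Let r = corr(characteristic, baseline), ρ = corr(baseline, follow-up) and s = SD(follow-up)/SD(baseline). Suppose the characteristic has no association with follow-up once baseline is known. Then

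corr(characteristic, change) = r(ρs − 1)/√(1 + s² − 2ρs),

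and the two-sided 5% rejection rate follows from Fisher's z, atanh|corr|×√(n − 3). The documents give no r, ρ or s, so all are assumed. For example, r = 0.2, ρ = 0.3, s = 0.5 gives 0.2×(0.15 − 1)/√0.95 = −0.174, z = 2.94, rejection 84%.

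| r | ρ = 0.8, s = 1 | ρ = 0.5, s = 1 | ρ = 0.3, s = 0.5 | ρ = 0, s = 0.3 |
|---|---|---|---|---|
| 0 | 5% | 5% | 5% | 5% |
| 0.1 | 8% | 13% | 31% | 36% |
| 0.2 | 19% | 39% | 84% | 90% |
| 0.3 | 36% | 71% | 99% | 99.9% |

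Small s, meaning strong suppression, gives the highest rates. With baseline added, simulated rejection (3,000 runs, r from 0 to 0.5; ρ = 0.5, s = 1 and ρ = 0.3, s = 0.5) was 4.5% to 5.6%.

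**HBeAg status and HBV DNA.** Assumptions: within-group baseline SD 1.2 log10; equal HBeAg groups; week-192 value independent of baseline, with 85% at 20 IU/mL (log10 ≈ 1.3) and the rest uniform from 1.3 to 4.

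- Follow-up variance = 0.15×2.7²/3 − (0.15×1.35)² = 0.3235, so SD 0.569.
- Gap 0.5: baseline SD = √(1.44 + 0.25²) = 1.226, r = 0.25/1.226 = 0.204, s = 0.464, corr = −0.204/√(1 + 0.464²) = −0.185, z = 3.13, rejection 88%.
- Gap 0.25: corr = −0.094, rejection 35% (34% to 35% by simulation).
- Gap 1: corr = −0.352, rejection 100%.
- In simulation, lowering the share at the floor to 60% gives 31%, 82% and 100% for the three gaps. The baseline-adjusted analysis stays at 4% to 5.5%.

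**Baseline against change.** With equal SDs, corr = −√((1 − ρ)/2): −0.71, −0.59, −0.50 and −0.32 for ρ = 0, 0.3, 0.5 and 0.8. This is built in and says nothing about response.

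**The direction can mislead.** Let two groups have the same 6 log10 drop, cut off at 20 IU/mL, with between-participant SD 1.1 and follow-up noise SD 0.5 (total √(1.21 + 0.25) = 1.208). Take baseline means of 6 and 7 log10, assumed for illustration. The share at the floor is Φ((1.301 − 0)/1.208) = 86% and Φ((1.301 − 1)/1.208) = 60%. Mean week-192 values after the cut-off are 1.39 and 1.65, so mean declines are 4.61 and 5.35. The higher-starting group declines 0.74 log10 more yet reaches the floor less often.

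**The case against.** **The regression may already be adjusted.** Initial HBV DNA is one of the plan's own baseline characteristics. If it enters the multiple regression, the other coefficients and p-values are identical whether the outcome is change or follow-up, because subtracting baseline shifts only the baseline coefficient, by −1. This stands: for HBV DNA the regression is silent, not wrong. It does not help the correlations, nor ALT, whose baseline value is in no list.

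**The figures are assumed.** The HBeAg rates correspond to a two-group comparison of change, equivalent to a Pearson correlation with a binary variable. The plan does not say it will correlate change with HBeAg status. Marked suppression is not the same as below 20 IU/mL, and early or off-treatment weeks may differ. Entry requires raised ALT, so the highest HBV DNA levels, which the Background places in the immune-tolerant phase, may be rare. All of this stands and limits the claim to what can happen.

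**Adjustment is not neutral.** Participants who start higher and reach the same floor did decline more. If a characteristic marks a stable difference in level with no effect on change (ρ = 0.5, s = 1), the raw correlation is correct at about 5%, while the adjusted test has partial correlation 0.5r/√((1 − r²)×0.75) and rejects 52%, 86% and over 99% in simulation for r = 0.2, 0.3 and 0.5. This has force for ALT. It fits HBV DNA under strong suppression poorly: in simulations of the 6 log10 scenario with baseline measurement error SD 0.4, adjusted rejection was 3% to 4% against 91% to 100% unadjusted. With only 44% to 52% at the floor it was 7% to 17% against 73% to 100%.

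**A stronger reading.** A reader might infer that the plan will report false predictors throughout, or that the arm comparison of change is biased. The documents support neither. Characteristics unrelated to baseline keep 5%, and under randomisation the between-arm t-test on change rejected 4.1% to 5.3% in every simulated setting.

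**Conclusion.** The concern holds in a limited form. The correlations of change are unadjusted as written, and the regression does not require the starting value. For HBV DNA, a characteristic related to baseline can be declared significant far more often than 5% solely because of where participants started: about 34% to 100% for assumed gaps of 0.25 to 1 log10 under strong suppression, and 8% to 36% for a weak link (r = 0.1) over the wider range of assumptions. These sizes rest on inputs the documents do not give.

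The consequence is modest. No continuous change score appears among the endpoints in Sections 2.2.1 to 2.2.9, so these are exploratory predictor analyses. The primary endpoint, the listed secondary endpoints and the between-arm comparisons are untouched. A rule that adjustment is always right cannot be extended to ALT, where the answer depends on whether one asks who changes more, or who changes more from a given start.

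**What to change.** In Section 8.1.2.1:

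- **HBV DNA regression:** list the covariates and always include day-0 HBV DNA. Change or follow-up may be the outcome, since the other coefficients are the same.
- **HBV DNA correlations:** replace the raw correlations with partial correlations given day-0 HBV DNA.
- **Baseline HBV DNA as a predictor:** relate it to the follow-up value or to the responder endpoints already defined (below 20 or below 1000 IU/mL), not to change.
- **Assay limit:** state how values below 20 IU/mL enter the change or follow-up value.
- **ALT:** report results adjusted for day-0 ALT alongside unadjusted results labelled descriptive, and state which question each answers.

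The cost is SAP wording and slightly more analysis. Day-0 HBV DNA and ALT are already collected, so no new data are needed. The downside is that results are less directly expressed as correlations with change.

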8.1.2.1. Analyses of other secondary endpoints

Secondary endpoints for this clinical trial are listed in sections 2.2.1 – 2.2.9. These endpoints could be grouped into several different classes. The first group of endpoints we will deal with are binary endpoints characterized by the occurrence of some event by a fixed time point. These events include HBeAg loss, HBeAg seroconversion, HBsAg seroconversion, normalization of ALT, ALT \leq 1.25 X ULN, HBV DNA $<$ 1000 IU/mL, HBV DNA $<$ 20 IU/mL, absence of detectable antiviral drug-resistance HBV mutations, treatment discontinuation, and treatment failure. Analysis will be conducted separately for these events at the designated time points listed in sections 2.2.1-2.2.9

Proportion of such an event (e.g. proportion of HBeAg loss) between two treatment groups will be summarized using 95% confidence intervals and will be presented graphically by using bar charts. The rate of occurrence of an event between two treatment groups will be compared using a two-sided two-sample proportion test (chi-square test or Fisher's exact test as appropriate). We will also describe the treatment effects using relative risk of the event and corresponding 95% confidence interval. In order to take into account the stratification at randomization, we will use Mantel-Haenszel chi-square test. Comparison of rates of an event across two treatment groups adjusting for other baseline demographic, virological and clinical characteristics such as

age, race, genotype, HBeAg status, initial HBV DNA level, and baseline histology will be performed using multivariable log-linear (Poisson) regression, with HBsAg loss (Yes/No) as the outcome. The results will be presented as relative risks of the event and their 95% confidence intervals.

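### The longitudinal models in section 8.1.2.1 adjust the arm comparison for unnamed post-randomisation characteristics, so their arm coefficient may not be the total effect of randomised treatment

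*Combined protocol and SAP*

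**What the plan says.** Section 8.1.2.1 sorts the remaining secondary analyses into three groups. The third covers "variables that are measured over time (longitudinal data) such as quantitative HBV DNA levels". Its purpose is stated as "To determine the significance of change in continuous outcome over time", and the sentence continues "across treatment group adjusting for other baseline and longitudinal participant characteristics". Mixed models are used for normally distributed data and GEE otherwise. The text then adds: "A similar approach of analysis will be adopted (generalized linear mixed model or GEE) for longitudinal binary or count outcomes over time". No longitudinal covariate is named, and no version of the model with baseline covariates alone is described.

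The other adjusted arm comparisons are worded differently. For binary endpoints the same section has "Comparison of rates of an event across two treatment groups adjusting for other baseline demographic, virological and clinical characteristics such as"; its examples are all fixed before treatment (histology, HBV DNA level at entry, HBeAg status, genotype, race and age). For time-to-event endpoints it has "Comparison of hazard rates of an event across two treatment groups adjusting for other baseline demographic, virological and clinical characteristics such as age, race" and the same remaining items. Section 8.1.2 (cumulative HBsAg loss) and section 8.2 (available-case analysis of the primary endpoint) also name baseline characteristics only.

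For changes in ALT and HBV DNA at designated time points, section 8.1.2.1 also plans a t-test or Wilcoxon test that "will be used to determine differences in the distribution of these changes between the two treatment arms", with no covariates.

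**The concern.** Randomisation makes the arms comparable at baseline. A covariate measured later can itself be a result of treatment, and holding it fixed in the model takes away whatever part of the treatment effect passes through it. If something unmeasured drives both the covariate and the outcome, conditioning on the covariate also brings in a spurious arm difference.

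The documents make such covariates available and the mechanism plausible:

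- Section 6.4 schedules ALT and HBV DNA at every on-treatment visit, and quantitative HBsAg and HBeAg from week 12.
- Section 1 says that HBsAg loss is distinctly greater with peginterferon, and that HBV DNA suppression usually precedes improvement in ALT.
- Section 1 also gives immune reactivity a governing role in the course of disease, and section 5.3.1 calls peginterferon immunomodulatory. A shared host cause is therefore conceivable.

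An ALT model adjusted for concurrent HBV DNA, or an HBV DNA model adjusted for HBsAg level, would fit the present wording. These are examples, not covariates that the plan lists. At stake is whether the arm effect reported from these models can be read as the effect of adding peginterferon. Because the covariates are open, their later selection could also influence the reported result.

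**Working it through.** **The plan's own figures.** The longitudinal models have no stated effect size or power. The sample size in the section on sample size and power (5% vs 15%, two-sided 5%, 80% power) reproduces at 141 per arm, and 282 / (1 - 0.25) = 376. It does not bear on this point.

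**Model.** Let M be a post-randomisation covariate, Y the outcome and U an unmeasured cause of both:

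- M = a·arm + gM·U + error (variance 1)
- Y = d·arm + b·M + gY·U + error

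The total randomised effect is d + a·b. In a model that includes M, the slope on M is b + gM·gY/(gM² + 1). The arm coefficient is therefore

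d + a·b - a·[b + gM·gY/(gM² + 1)] = d - a·gM·gY/(gM² + 1).

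Without a shared cause this is simply d.

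**Inputs.** All values of a, b, d, gM and gY are assumptions in SD units, because the documents give none.

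| Setting | a | b | d | gM = gY | Total effect | Arm coefficient adjusted for M |
|---|---|---|---|---|---|---|
| 1. Fully mediated | -0.5 | 0.6 | 0 | 0 | -0.30 | 0.00 |
| 2. Partly mediated | -0.5 | 0.6 | -0.2 | 0 | -0.50 | -0.20 |
| 3. Fully mediated, shared cause | -0.5 | 0.6 | 0 | 0.7 | -0.30 | +0.16 |
| 4. Partly mediated, shared cause | -0.5 | 0.6 | -0.2 | 0.7 | -0.50 | -0.04 |
| 5. Opposing direct effect | -0.5 | 0.6 | +0.1 | 0 | -0.20 | +0.10 |
| 6. M not affected by arm | 0 | 0.6 | -0.3 | 0.7 | -0.30 | -0.30 |
| 7. M unrelated to Y | -0.5 | 0 | -0.3 | 0 | -0.30 | -0.30 |

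Arithmetic for the main settings:

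- Setting 1: total 0 + (-0.5 × 0.6) = -0.30; adjusted 0.
- Setting 2: total -0.2 - 0.30 = -0.50; adjusted -0.2. The loss is 0.30/0.50 = 60%.
- Setting 3: 0.49/1.49 = 0.329, and 0 - (-0.5 × 0.329) = +0.164.

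**Check in the planned model types.** The simulation used 188 per arm and six visits, with GEE under an independence working correlation (100 runs) and a random-intercept mixed model (40 runs). The arm effect was held constant across visits.

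| Setting | GEE without M | GEE with M | Mixed model with M | GEE runs with p < 0.05, without M → with M |
|---|---|---|---|---|
| 1 | -0.300 | -0.001 | 0.002 | 97% → 9% |
| 2 | -0.496 | -0.196 | -0.185 | 100% → 86% |
| 3 | -0.308 | +0.163 | +0.046 | 60% → 51% |
| 6 | -0.310 | -0.303 | -0.302 | 60% → 92% |

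In setting 3 the mean estimate with M has the wrong sign. In every setting the model without M recovers the total effect to within simulation error.

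**The case against.** **The covariates are unnamed, so the bias may not arise.** This stands in part. Settings 6 and 7 show no bias when arm does not affect the covariate, or when the covariate is unrelated to the outcome and no cause is shared. Setting 6 even shows a gain in precision. Both arms also receive tenofovir, and section 1 expects marked HBV DNA suppression in 80-90% of patients on long-term treatment with such agents, so the arm effect on HBV DNA could be small. But the plan contains no restriction to harmless covariates. Nor is visit time a natural meaning of participant characteristics.

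**The reach is narrow.** This stands. The primary endpoint is compared by an unadjusted two-sample proportion test (section 8.1.1). The endpoints listed in section 2.2 are binary responses, cumulative rates or event rates, and none is a repeated-measures trajectory. Fixed-time and time-to-event analyses use baseline covariates only. For HBV DNA, the example outcome in the third group, an unadjusted comparison of changes is also planned. That comparison does not repair the longitudinal estimate, and no rule says which result prevails if they disagree.

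**Post-baseline covariates help with dropout.** Section 8.2 already assigns that task to likelihood methods and, for GEE, to inverse-probability weighting. Post-baseline variables can enter the weight model without changing what the arm coefficient means.

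**A stronger reading.** A reader might infer that these models will hide the peginterferon effect, or show harm where there is benefit. The documents do not support that. Reversal needs an unmeasured shared cause or an opposing direct effect, and nothing in the plan shows that either will occur. Even in setting 3 the mixed model, the plan's choice for normal data, moved only to about +0.05.

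**Conclusion.** The point holds as a defect in the stated rule for one class of secondary analyses. As written, the longitudinal models may adjust the arm comparison for variables that treatment has changed. Where such a variable is also related to the outcome, the coefficient is not the total randomised effect: the mediated part can be lost, and the sign can change if a cause is shared.

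Confidence is high in the mechanism, which follows from the algebra. It is low in any size or direction for this trial, because the covariates and their effects are not given. The figures of -0.30 to 0.00 and -0.50 to -0.20 rest wholly on the assumed a = -0.5 and b = 0.6, with d = 0 and d = -0.2 respectively and no shared cause.

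The primary analysis, the sample size, the fixed-time binary and time-to-event analyses, and the unadjusted comparison of changes at designated time points are untouched. The correction should be made, but the trial's main conclusion does not depend on it.

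**What to change.** In the third group of section 8.1.2.1, for every longitudinal model used to report an arm effect (continuous, binary or count), replace the reference to baseline and longitudinal characteristics with *the randomisation strata and pre-specified baseline characteristics*. State that the model contains arm, time and arm-by-time terms. The strata are those already used at randomisation: HBeAg status, genotype A vs others, and cirrhosis.

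Any model with time-varying post-randomisation covariates can stay as a separately labelled exploratory or mediation analysis, with a note that its arm coefficient is not read as the total treatment effect.

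The cost is about one sentence of SAP wording, plus fixing the baseline covariate list before analysis. No new data, visits or participants are needed.
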